COMIRB 19-0402

PI: [name]

Version Date: December 6, 2023

SARC Approved 5/8/2019

***Per-oral Pancreatoscopy-guided Lithotripsy vs. Extracorporeal Shock Wave
Lithotripsy For Treating Symptomatic Main Pancreatic Duct Stones in Chronic
Pancreatitis: A Multicenter Randomized Clinical Trial***

Lead Site: University of Colorado

Version Date: December 6, 2023

Table of Contents

Table of Contents.....	2
Synopsis	3
List of Abbreviations	4
Study Protocol.....	5
Research Questions and Hypothesis	5
Basic Design of the Study	7
Sample and Methodology	7
Subject Inclusion and Exclusion Criteria	9
Inclusion Criteria:	9
Exclusion Criteria:	9
Study Steps	10
Screening/Baseline Evaluation	10
Consent	10
Randomization	10
Treatment Regimens	10
Outcome Determination	11
Standard of Care/Research Procedure.....	12
Subject and Study Stopping Criteria.....	12
Data Collection Tool	13
Data Analysis Plan	13
Data and safety monitoring plan.....	14
Definition of AEs, serious AEs, and unanticipated problems	14
Procedures for documentation of adverse events	15
Monitoring of Data	16
Feasibility/Recruitment Plan/Materials	16
Training Plan.....	16

Synopsis

Title	Per-oral Pancreatoscopy-guided Lithotripsy vs. Extracorporeal Shock Wave Lithotripsy in Chronic Pancreatitis: A Multicenter Randomized Clinical Trial
Investigative sites	University of Colorado The Ohio State University Baylor St. Luke's Medical Center Methodist Dallas Medical Center University of Minnesota University Health, San Antonio Indiana University Washington University School of Medicine
Hypothesis	The central hypothesis is that per-oral pancreatoscopy- guided lithotripsy is superior to extracorporeal shock wave lithotripsy in clearance of main pancreatic duct stones, thereby improving pain levels and quality of life in patients with chronic calcific pancreatitis.
Primary Objective	To demonstrate the superiority of per-oral pancreatoscopy over extracorporeal shock wave lithotripsy in clearance of main pancreatic duct stones in patients with chronic pancreatitis. Failure to remove any or all stones with the initial intervention will be an outcome recorded for the study.
Secondary Objective	To demonstrate the effect of stone clearance to reduce pain and opiate use and improve quality of life.
Timeline	Enrollment will be performed over a 24-month time period with follow-up performed at 1, 3, 6, 12, 18, and 24 months after ductal clearance.

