Following complete PD stone removal, patients will be given a validated quality-of-life instrument, the PANQOL¹⁸, at 1, 3, 6, 12, 18, and 24 months post-treatment. Similarly, the visual analog scale will also be given at 1, 3, 6, 12, 18, and 24 months post-treatment. Lastly, daily opiate use will be recorded at 1, 3, 6, 12, 18, and 24 months post-treatment. The 1, 3, 6, 12, 18, and 24-month assessments will have a ± 2 weeks window to be completed.

In order to ensure that subjects respond to the questionnaires as required, REDCap will be programmed to automatically send three reminders to the participants' email when the questionnaires are due. Furthermore, the study coordinator will make three separate attempts to contact non-responding patients within the designated timeframe. If a patient remains unresponsive, these instances will be documented as protocol deviations.

Documentation on interventions for chronic pancreatitis occurring outside of scheduled appointments will be recorded a separate CRF ("non-scheduled chronic pancreatitis interventions"). This CRF will encompass any pancreatic interventions (other than POP x ESWL planned visits) taking place between the subject's consent form signature and their final follow-up.

All patients will have a HgbA1c and fecal elastase drawn at baseline (within 12 months prior to treatment initiation) and at the 1-year mark from treatment completion. Laboratory tests will be drawn per standard of care, and tests results will be added to the REDCap database.

Figure 1: Study Flowsheet

4. Subject Inclusion and Exclusion Criteria

4.1 *Inclusion Criteria:*

1. Subjects aged 18-89
2. Subjects with abdominal pain secondary to chronic calcific pancreatitis and main pancreatic duct stones found on cross-sectional imaging, EUS, or ERP with upstream PD dilation
3. Main PD stones in the head or body that are greater than 50% in size of the immediate downstream diameter of the pancreatic duct
4. Stones ≥ 5 mm in diameter or impacted in the main PD on cross-sectional imaging or EUS

4.2 *Exclusion Criteria:*

1. Subjects who have previously received PPL or ESWL for PD stones within 12 months of enrollment
2. Patients with PD stones isolated in the tail or side branches of the main duct
3. Pancreatic tail stones comprising more than one-third of the stone burden within the main PD, if multiple locations of stones are noted within the main PD
4. Nontraversable ansa loop with upstream stones

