Subjects may withdraw from the study at any time for any reason. Subjects can also be withdrawn from the study at any time at the discretion of the investigators for breach of study protocol or emergence of an exclusion criteria (i.e. pregnancy).

The study can be stopped at any point should the Data Safety Monitoring Board (DSMB) request cessation

of the trial based on any compilation of adverse events or clear demonstration of superiority of one technique. Similarly, should the interim analysis reveal futility in that the study hypothesis is deemed unprovable within the constraints of the study, the study may be stopped. The study will also be stopped once the intended sample size goal is reached and 6-month follow-up has been obtained. Lastly, the study can be stopped should study costs exceed the allotted budget.

8. Data Collection Tool

A comprehensive system has been previously developed at this institution, and will support the data collection and reporting needs of this project which includes:

- (i) streamlining data collection from the participating centers,
- (ii) creating a secure database from which statistical analysis can be performed. Data will be stored at the University of Colorado instance of REDCap15, which resides on a local secure server. Data regarding stone clearance rates and adverse events will be entered by investigators at each center. Using an Application Programming Interface (API), data can be transferred to and from REDCap to SAS software (v.9.3, SAS Institute, Cary, NC) used to export data from REDCap to SAS to conduct analysis. SAS software interfaces seamlessly with REDCap-produced syntax files (i.e. SAS code) and SAS-ready CSV (comma separated variables) data files. Results of these analyses will be imported back into REDCap, using the API, for long-term storage, reference, and further analysis. Access to these data will be controlled by a custom module and all users of the site will be required to log in. No protected health information will be collected or displayed and data stored in our HIPAA compliant serve environment to ensure privacy.

9. Data Analysis Plan

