All serious AEs that occur from initiation of the study to 14 days post final intervention are to be reported immediately (within 24 hours) using the electronic data collection system. All serious AEs will then be immediately relayed to the PIs. The PIs will first review the AEs to: 1) ascertain the seriousness, 2) ascertain the relationship between AE and intervention, 3) verify that all data are complete, and 4) follow-up with the specific site for incomplete data and/or data clarification. The PIs will then submit the AEs to the DSMB, who will then review the AEs to confirm the findings of the PIs.

All AEs from ESWL are ESWL-related. PPL is part of the ERCP procedure. Most AEs in this group will be related to the ERCP procedure itself. A potential rare AE specific to PPL (EHL or LL) is ductal perforation from the lithotripsy fiber and will be noted by the investigator. The investigator will determine the relationship of an AE specific to a lithotripsy device used to fragment the stones.

10.3 *Monitoring of Data*

The DSMB will be responsible for data and safety monitoring. All primary and secondary outcomes as well as data integrity and study progress along with all AEs will be reviewed by the DSMB.

The DSMB will meet at least twice a year to review the data mentioned above. These meetings will every six months.

An interim analysis will be performed at the halfway point of enrollment, which is expected to be at the 75th patient. Should the interim analysis reveal an unexpected accumulation of AEs or a clear superiority of one lithotripsy method over the other, the DSMB may recommend stopping the study, which will be reported to the PIs, IRB and the funding agency.

The DSMB will include at a minimum the following individuals:

- [name]: Gastroenterologist, University of Colorado
- [name]: Hepatologist, University of Colorado
- Biostatistician: Non-study Statistician
- [name]: Gastroenterologist, Beth Israel Deaconess Medical Center

11. Feasibility/Recruitment Plan/Materials

The power analysis suggests that a total of 150 participants will need to be enrolled to achieve sufficient statistical power to compare the two lithotripsy methods. With a total of 8 recruitment sites, we anticipate complete enrollment within 5 years and with a follow-up of 12 months/patient post completion of treatment, the study is anticipated to be completed within 6 years.

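### Section 7 closes the study at 6-month follow-up, which contradicts the 24-month visit schedule, the 1-year laboratory tests and the 12 months per patient in Section 11

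*Combined protocol and SAP*

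**What the plan says.** The plan gives three follow-up lengths and two enrolment lengths.

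- **Section 7 (stopping criteria):** "The study will also be stopped once the intended sample size goal is reached and 6-month follow-up has been obtained". This sentence is mandatory, whereas the neighbouring provisions on DSMB request, futility and budget are permissive. It does not say whose 6-month follow-up triggers the stop.
- **Synopsis, Timeline:** "Enrollment will be performed over a 24-month time period with follow-up performed at 1, 3, 6, 12, 18, and 24 months after ductal clearance".
- **Section 3 (sample and methodology):** the quality-of-life instrument is given as "the PANQOL¹⁸, at 1, 3, 6, 12, 18, and 24 months post-treatment"; for pain, "the visual analog scale will also be given at 1, 3, 6, 12, 18, and 24 months post-treatment"; and "daily opiate use will be recorded at 1, 3, 6, 12, 18, and 24 months post-treatment". The timing rule includes month 24: "24-month assessments will have a ± 2 weeks window to be completed". HgbA1c and fecal elastase are required for all patients at baseline and again "at the 1-year mark from treatment completion".
- **Section 11 (feasibility):** enrolment within 5 years, "with a follow-up of 12 months/patient post completion of treatment", and completion within 6 years.

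Section 2 lists stone recurrence as a major secondary endpoint. Section 9 adds hospitalisations related to chronic pancreatitis over a follow-up period that it does not define. It compares categorical outcomes by chi-squared or Fisher's exact test and continuous ones by Student's t test. Nothing says that patients already enrolled continue after the Section 7 stop, or that the later visits are optional.

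**The concern.** For a patient enrolled near the end, a site cannot obey both Section 7 and Section 3. Following Section 7 ends that patient's participation before month 12, and so before the 1-year laboratory tests, month 18 and month 24. Visits not made before close-out cannot be recovered.

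Two consequences follow for the analysis. First, scheduled data on pain, quality of life, opiate use and the two laboratory tests are lost for part of the sample, and Section 9 names no time point at which changes are to be compared. Second, recurrence and hospitalisation are counted over whatever time each patient was observed. Under Section 7 that runs from 6 months for the last patient to 24 months for early ones, and the planned tests make no allowance for unequal exposure.

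**Working it through.** **1. The plan's own timeline.** Section 11 implies 60 + 12 = 72 months, which reproduces its 6 years but leaves no time for treating the last patient. The Section 7 rule gives 60 + 6 = 66 months. The full visit schedule needs 60 + 24 = 84 months with 5-year enrolment, or 24 + 24 = 48 months with the Synopsis enrolment period. All are before treatment time.

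**2. Inputs.** N = 150 (Sections 3 and 9). Enrolment E = 60 months (Section 11) or 24 months (Synopsis). Visits v = 12, 18, 24 months (Synopsis, Section 3). Follow-up at the stop s = 6 months (Section 7) or 12 months (Section 11).

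**3. Assumptions, because the documents do not give them.** Accrual is uniform, the time from enrolment to the end of treatment is similar for all patients, and the stop falls at the last patient's 6-month visit. The last is the most favourable reading of Section 7; any earlier trigger loses more.

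**4. Formula.** A patient enrolled t months before the last one has s + t months of follow-up at the stop. Visit v is out of reach when t < v − s, so the share lost is (v − s)/E and the number lost is 150 × (v − s)/E.

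**5. Results, before dropout.**

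| Stop rule | Enrolment | Month 12 | Month 18 | Month 24 |
|---|---|---|---|---|
| s = 6 (Section 7) | 60 months | 6/60 = 10% (15) | 12/60 = 20% (30) | 18/60 = 30% (45) |
| s = 6 (Section 7) | 24 months | 6/24 = 25% (about 38) | 12/24 = 50% (75) | 18/24 = 75% (about 113) |
| s = 12 (Section 11) | 60 months | 0 | 6/60 = 10% (15) | 12/60 = 20% (30) |
| s = 12 (Section 11) | 24 months | 0 | 6/24 = 25% (about 38) | 12/24 = 50% (75) |

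The month-12 column also applies to the 1-year laboratory tests.

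**6. Base for the counts.** Section 3 starts the questionnaires and opiate records after complete clearance, and recurrence presupposes clearance. At the planning rates in Section 9, 75 × 0.70 + 75 × 0.90 = 52.5 + 67.5 = 120 patients would clear. On that base the 5-year losses under Section 7 are 12, 24 and 36 patients; the percentages do not change. Section 9 also plans to examine these outcomes in patients with only partial clearance, so the intended base is unclear. For the laboratory tests, which are for all patients, 150 is the right base.

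**7. Visit window.** If every visit were made 2 weeks early, the share becomes (v − 0.5 − 6)/E. Of 150, that gives about 14, 29 and 44 (5 years) or 34, 72 and 109 (24 months). The window changes little.

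**8. Primary endpoint.** Section 9's 62 per arm (124 in total) reproduces for 70% versus 90%, two-sided 0.05 and 80% power, with pooled variance and no continuity correction; power at 62 per arm is 80.3%. Follow-up length does not enter this calculation.

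**The case against.** The strongest reply is that the trial's main result is safe. Complete clearance is judged on the pancreatogram at treatment completion, so no close-out date in dispute changes that endpoint, its power or the sample of 150. This stands, and it limits the severity.

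Five stronger readings are tempting, and the documents do not support them.

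- **That the stop biases the comparison.** The cut is administrative, and under 1:1 randomisation it should fall about equally on both arms. Follow-up starts after treatment, and up to four sessions are allowed, so an arm that takes longer to finish could be observed for less time. The documents give nothing to quantify this. It is a possibility, not a demonstrated bias.
- **That Aim 2 fails because durability cannot be shown.** The aim is to reduce pain and improve quality of life. No durability objective is stated, and no later month is named for analysis.
- **That late visits would contain only a small early group.** With 5-year enrolment, 90%, 80% and 70% of patients can still reach months 12, 18 and 24.
- **That up to three quarters of the 24-month data are lost.** This follows only from the Synopsis enrolment period, which conflicts with Section 11's more detailed timeline. It is the upper end of the range.
- **That moving the stop to 12 months cures everything.** It completes month 12 and the laboratory tests, but months 18 and 24 remain incomplete.

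It is also fair to say that the length of follow-up is the sponsor's choice. That does not remove the contradiction: the plan has to state one choice.

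**Conclusion.** The contradiction is real and nothing in the documents resolves it. As written, Section 7 discards scheduled secondary-endpoint and 1-year laboratory data and leaves recurrence and hospitalisation observed for unequal times, under tests that ignore this. On Section 11's enrolment period the loss is about 10%, 20% and 30% at months 12, 18 and 24. On the Synopsis's period it is 25%, 50% and 75%. These figures rest on uniform accrual, similar treatment times and a stop at the last patient's 6-month visit; they precede the 20% dropout that Section 9 expects. The harm is lost precision and an undefined comparison time for secondary outcomes. A reader might infer that the primary conclusion or the balance between arms is compromised; the documents do not show either. This should be fixed, but it does not threaten the primary analysis.

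**What to change.** Reconcile the Synopsis, Section 3, Section 7 and Section 11 in one amendment.

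1. **Section 7:** change the close-out from 6-month follow-up to at least the last patient's 12-month follow-up after treatment completion, which matches Section 11. State any extra time needed to treat the last patient, since 60 + 12 = 72 months has no room for it.
2. **Enrolment period:** give the same figure in the Synopsis and Section 11.
3. **Section 9:** compare secondary outcomes, including recurrence and hospitalisation, at a time point that all patients can reach. Under the rule above that is month 12.
4. **Months 18 and 24:** either treat them as administratively censored at study close or, if 24-month conclusions are wanted, run to the last patient's 24-month visit and restate the timeline as at least 84 months with 5-year enrolment.

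The cost is the amendment and a close-out about 6 months later than Section 7 (72 rather than 66 months), roughly what Section 11 already plans. Under the 12-month option with 5-year enrolment, months 18 and 24 still lose about 10% and 20% of patients. The sample size does not change.

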ESWL will start at the lowest power level and will gradually be increased until 25% of the shocks have been delivered to help create vascular constriction to minimize the risk of hematoma. The middle 50% of the shocks will be equally distributed between the 1st 25% of shocks and the final 25% of shocks at the top level of power. The final 1000 shocks should be administered at the highest power level number. The range of shocks delivered will be limited to 4000 to 6000 shocks. The rate of shocks will range from 70-90/minute.

A KUB (kidney-urether-bladder)-right posterior oblique X-ray will be done within 7 days after the ESWL session to determine the level of fragmentation of the stones. The goal will be to continue ESWL until stone fragments are felt to be \leq 3mm.

Non-lithotripsy panreatoscopy maneuvers will be permitted in the ESWL arm and not result in primary endpoint failure.

5.5 *Outcome Determination*

An occlusion panreatogram following extraction of stone fragments will be obtained after the endoscopist/urologist has determined treatment completion. All patients will receive an ERP at the completion or either PPL or ESWL, with an occlusion panreatogram performed to determine stone

clearance. An initial pancreatogram (or PD image from cross-sectional test – MRCP, MRI, CT scan, or EUS) with stone location and two representative final occlusion pancreatogram images will be uploaded to the REDCap database and will be reviewed by a blinded endoscopist to assess the level of stone clearance (complete or partial).

6. Standard of Care/Research Procedure

The current standard of care for the treatment of PD stones varies by region. In Europe, extracorporeal shock- wave lithotripsy (**ESWL**) is a primary method by which stones are fragmented. Once ESWL is performed, however, ERP is still performed to remove the stone fragments. In Europe, ESWL is frequently performed by gastroenterologists who can perform ERP as well.

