In the United States, however, ESWL is primarily performed by urologists for the treatment of kidney stones. Few gastroenterologists have direct access to ESWL and urologists remain hesitant to use ESWL for non-kidney stones. Therefore, in the United States, standard therapy has become ERP.⁴ In ERP, pancreatography is performed by cannulating the PD and then injecting radio-opaque iodine contrast into the PD. Pancreatography allows for radiographic visualization of a stone and associated strictures; stone removal can be achieved by sweeping the PD with either a balloon or basket after performing a pancreatic sphincterotomy where the sphincter opening the PD is cut and coagulated. This is often followed by balloon or catheter dilation of any downstream pancreatic duct strictures. ERP is typically made more difficult by strictures downstream of the stones and the presence of numerous, large (>5mm in diameter) or hard stones.

In this study, per-oral pancreatoscopy-guided lithotripsy (**PPL**) will be compared with ESWL. Pancreatoscopy, the placement of a small endoscope directly into the PD, allows for direct visualization of the PD and stones. This allows for intraductal lithotripsy to be performed while directly visualizing the stones. Briefly, EHL, one version of intraductal lithotripsy, creates high-frequency shock-wave pulses which generate energy that can result in the fragmentation of stones. LL, on the other hand, involves the focusing of laser light on the surface of a stone which can induce wave-mediated stone fragmentation. Both techniques can fragment stones into smaller pieces, which can then be swept out of the PD using standard techniques such as balloon or basket sweeping.

Upon completion of the procedure, all patients will be observed in the post-anesthesia care unit for 1 hour as is the current standard of care. Following the index ERP session and sphincterotomy, extended recovery in the hospital or discharge will be planned per institutional practice. If patients exhibit symptoms such as intractable abdominal pain or severe N/V, they will be admitted for overnight observation. All patients will receive a phone call within 48 hours of discharge as is standard practice to identify any short-term AE's.

7. Subject and Study Stopping Criteria

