Statistical Analysis: Comparison of technical success rate, defined as the rate of complete clearance of PD stones, between PPL and ESWL will be performing using the chi-squared test or Fisher's exact test. Secondary outcomes including adverse event (both overall and serious adverse event) rates, procedure length, and number of procedures will be compared using a chi-square test or Fisher's exact test for categorical variables and the Student's t test will for continuous variables. A p value <0.05 will be considered significant. In the primary analysis, all results will be analyzed under an intention-to-treat protocol. A per-protocol (secondary) analysis will also be performed where the technical success will be attributed to the combination of modalities resulting in achieving the primary outcome should cross-over occur.

To identify predictors for technical success, a multivariable logistic regression will be performed incorporating variables that were associated ($p<0.2$) with technical success on univariate analysis.

In terms of secondary outcomes, change in PANQOLI scores, VAS scores, and opiate daily doses will be compared between subjects in the PPL group and ESWL group. Additional outcomes to be measured include stone recurrences and number of chronic pancreatitis-related hospitalizations during the follow-up period. Should cross- over occur, under the primary (intention-to-treat) analysis, the outcomes will be attributed to the initially randomized intervention. In the secondary (per-protocol) analysis, the outcomes will be attributed to the combination of treatments resulting in technical success. A subgroup analysis will also be performed on patients who achieved only partial stone clearance (thus considered a treatment

failure) in the above-mentioned outcomes. Comparisons will be made using a chi-squared test or Fisher's exact test for categorical variables and the Student's t test for continuous variables. Paired t tests will be performed to evaluate individual changes within each arm. A p value <0.05 will be considered significant.

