Power analysis: A large meta-analysis by Moole et al found a complete stone clearance rate of 70% in patients who received ESWL in conjunction with ERCP.¹⁴ In contrast, the largest studies examining pancreatoscopy-guided lithotripsy methods have found complete stone clearance rates ranging from 83-99%.^{6,17} Using a conservative stone clearance rate of 90% for pancreatoscopy- guided lithotripsy, a sample size calculation was performed using a two-sided test with 80% power and significance (α) of 0.05. This demonstrated the need for 124 subjects total, with 62 in each arm. Accounting for an expected dropout rate of 20%, the sample size needed would be a total of 150, or 75 subjects in each arm.

10. Data and safety monitoring plan

A Data and Safety Monitoring Board (DSMB) will be established to monitor the data and safety of this project. A DSMB will be appointed by the study team and will include at a minimum: A senior faculty member clinician with substantial research experience within the Division of Gastroenterology and Hepatology at the University of Colorado who is not involved in the study, and will serve as the group leader, a statistician, and a senior gastroenterologist from a non- participating academic institution. The DSMB will meet every six months. DSMB meetings will be only open to designated DSMB staff and other individuals who have been approved to have access to unblinded data. Any recommendations for alteration or termination for part or all of the trial shall be based on consideration of the accumulating data in the context of totality of evidence. Specific statistical monitoring guidelines for safety and efficacy concerning the primary and secondary endpoints will be developed in cooperation with the DSMB.

10.1 *Definition of AEs, serious AEs, and unanticipated problems*

AEs are defined as any undesired, harmful, or pathological change in a patient as indicated by signs, symptoms, or laboratory changes that occur in association with the use of the trial interventions, whether considered intervention-related or not. This definition includes intercurrent illness or injuries, exacerbation of existing conditions, psychological events, psychosocial events, and AEs as a result of the study intervention. All endoscopic AEs will be defined and classified as recommended by the American Society for Gastrointestinal Endoscopy (ASGE).²⁰

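### The primary clearance test is left open between chi-squared and Fisher's exact test; only Pearson chi-squared reaches the stated 80% at 62 per arm, and prespecified adjustment for stone characteristics is an unused option

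*Combined protocol and SAP*

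**What the plan says.** Section 9 (Statistical Analysis) states that the comparison of complete clearance "between PPL and ESWL will be performing using the chi-squared test" or Fisher's exact test, by intention to treat at p<0.05. It gives no criterion for choosing between the tests, and no covariate enters the comparison. The only multivariable model is a separate logistic regression for predictors of technical success, with variables screened at p<0.2.

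The power paragraph takes the ESWL rate from a meta-analysis that "found a complete stone clearance rate of 70% in patients who received ESWL in conjunction with ERCP" and assumes 90% for PPL. It says that "a sample size calculation was performed using a two-sided test with 80% power and significance (α) of 0.05", and concludes: "This demonstrated the need for 124 subjects total, with 62 in each arm". Enrolment is then set at 150 to allow for 20% dropout.

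Section 5.3 specifies 1:1 randomisation and names no stratification factor.

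On stone characteristics:
- Section 4.1 requires "Main PD stones in the head or body that are greater than 50% in size of the immediate downstream diameter of the pancreatic duct", and stones that are at least 5 mm or impacted.
- Section 5.5 provides for an initial image "with stone location and two representative final occlusion pancreatogram images will be uploaded to the REDCap database".
- Section 6 remarks that "ERP is typically made more difficult by strictures downstream of the stones and the presence of numerous, large (>5mm in diameter) or hard stones".
- Section 1 says that existing methods work less well on larger, impacted stones. It mentions heavy impacted burden in the head only as a special case.

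**The concern.** There are two issues of different weight.

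First, an open choice between two primary tests leaves the trial's power undefined and allows the choice to be made after the data are seen. The tests can disagree. Every table that Fisher calls significant here is also significant by Pearson, but the reverse does not hold.

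Second, the protocol treats stone burden as relevant to how hard removal is, and eligibility requires it to be assessed. Yet this information is kept out of the treatment comparison and used only in a data-driven predictor model. With no stratification stated, chance imbalance in stone burden adds noise to the observed difference, and neither design nor analysis removes it. Prespecified adjustment would recover some of that precision without more patients.

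**Working it through.** **Inputs.** 70% and 90% clearance, two-sided 0.05, 80% power, 62 per arm evaluable, 75 per arm enrolled, 20% dropout (all Section 9). Dropout at the stated rate leaves 150 × 0.8 = 120, or 60 per arm.

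**Reproducing the plan's figure.** With the pooled normal approximation and no continuity correction,

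n = [1.960 √(2 × 0.8 × 0.2) + 0.842 √(0.7 × 0.3 + 0.9 × 0.1)]² / 0.2²
= [1.960 × 0.5657 + 0.842 × 0.5477]² / 0.04
= 61.6, rounded up to 62.

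This matches the plan. The continuity-corrected formula would give 72 per arm. The stated size was therefore derived for the uncorrected chi-squared.

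**Exact power of the two named tests.** Sum the product of the two binomial probabilities over every pair of counts at which the test rejects:

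| Per arm | Pearson | Fisher | Difference (points) |
|---|---|---|---|
| 60 | 80.2% | 73.0% | 7.2 |
| 62 | 81.0% | 74.9% | 6.1 |
| 75 | 88.5% | 83.7% | 4.8 |

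Because Fisher's rejections are a subset of Pearson's, the last column is also the chance that the tests disagree under the design alternative. The continuity-corrected chi-squared has the same power as Fisher at all three sizes, so the word uncorrected matters.

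**Does validity require Fisher?** The exact type I error of Pearson at 62 per arm is 4.7% when both rates are 80%, and 4.7% to 5.1% for common rates between 70% and 90%. It does not.

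**Gain from adjustment.** The documents give no odds ratio, explained variance or clearance rate by stone size or location, so prognostic strength is an assumption shown as a range. Simulation: two normal baseline covariates, marginal rates held at 70% and 90%, adjusted score test against unadjusted Pearson, 8,000 trials per setting.

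| Combined log-odds SD (assumed) | Gain at 62 per arm (points) | Gain at 75 per arm (points) |
|---|---|---|
| 0 | 0.4 | about 0 |
| 0.3 | 0.9 | 0.2 |
| 0.6 | 2.8 | 1.4 |
| 0.8 | 3.6 | 2.1 |
| 1.0 | 5.3 | 3.1 |

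Each simulated power at 62 per arm has a standard error of about √(0.8 × 0.2 / 8,000) = 0.45 points, so the smallest gains are not distinguishable from zero. Other runs of the same design put the top row at 5.5 points (80.8% to 86.3%) at 62 per arm and about 4 at 75.

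**Cross-check.** Use an effective size n/(1 − R²), where R² is the assumed share of outcome variance explained. From the approximate base of 80.3% at 62 per arm:
- R² of 0.02 gives 62/0.98 = 63.3 and 81.1% (+0.8).
- R² of 0.05 gives 65.3 and 82.3% (+2.0).
- R² of 0.10 gives 68.9 and 84.3% (+4.0).
- R² of 0.15 gives 72.9 and 86.3% (+6.0).

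At 75 per arm (base 87.2%) the gains are +0.7, +1.6, +3.2 and +4.8. The last is slightly above the simulated range because R² of 0.15 is a strong assumption.

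**Room for covariates.** Expected failures are 62 × 0.3 + 62 × 0.1 = 24.8 at 62 per arm, and 75 × 0.3 + 75 × 0.1 = 30 at 75.

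**The case against.** The strongest reply has four parts.

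- **The plan is internally sound for Pearson.** The unadjusted chi-squared holds its type I error and meets its target at 62 per arm. Convention reserves Fisher for expected counts below 5, and about 24.8/2 = 12.4 failures per arm are expected under a common rate. This stands, and it is why the adjustment part is not an error. But the plan states no such rule, and writing one down costs nothing.
- **Fisher is adequate at full enrolment.** At 75 per arm it has 83.7% power. That is correct. A reader might infer that Fisher leaves the trial underpowered at any size; the figures do not support that. The shortfall arises at 62 and 60 per arm.
- **The covariates may be weak.** The remark in Section 6 concerns conventional ERP extraction, not clearance after lithotripsy. Eligibility already restricts patients to stones of at least 5 mm or impacted, mainly in the head or body, which narrows the spread of both factors. Location is barely supported as prognostic. All this stands and pushes towards the low end of the range. It does not remove the point, because uninformative covariates cost almost no power.
- **The data are not all in hand.** Criterion 4 can be met by impaction alone, the baseline list in Section 5.1 has no stone diameter, and Section 5.5 asks for an image from any of several modalities. It would be wrong to infer that a change of wording suffices.

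Part of the simulated gain may also reflect a slightly liberal test: the adjusted score test's type I error was about 5.1% to 5.7%.

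**Conclusion.** The concern holds in two parts. The firm part rests only on the plan's own rates and sizes: the stated 80% at 62 per arm is true for uncorrected Pearson (81.0%) and not for Fisher (74.9%), and the plan allows either. The softer part is a missed efficiency gain of roughly 0 to 6 points at 62 per arm, or about 0 to 4 at 75, for an assumed combined log-odds SD between 0 and 1.0.

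A reader might infer that the unadjusted test definitely forgoes 3 to 6 points. The documents do not support that. It is the upper part of the range and needs stone characteristics to explain about 7% to 15% of outcome variance, a figure found nowhere in the protocol. Nor do they support calling the unadjusted analysis invalid. The change is worth making, but the trial's validity does not depend on it.

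**What to change.** In Section 9, state one primary test: logistic regression of complete clearance on arm plus two baseline stone covariates, with arm tested by the score test. Size and impaction have the better support in the protocol; location is a possible second choice. Report a standardised risk difference with a 95% confidence interval, because the adjusted odds ratio is a different quantity from the difference used to size the trial. Keep the unadjusted, uncorrected Pearson chi-squared as a sensitivity analysis, and delete Fisher's exact test for the primary endpoint. Keep this model separate from the p<0.2 predictor screen.

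Fix the covariates before any outcome is unblinded, including for the interim analysis in Section 10.3, expected at the 75th patient.

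Costs are small, but there are some:
- Stone diameter, if used, needs a data field, a simple measurement rule across imaging types and a rule for missing values.
- With about 25 to 30 failures expected, the model should stay at two covariates.
- Type I error may sit slightly above 5%, which the Pearson sensitivity analysis helps to put in context.

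If the sponsor prefers not to adjust, naming uncorrected Pearson alone would still resolve the firm part of the point.
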